4. ELIGIBILITY CRITERIA

4.1 INCLUSION CRITERIA

No waivers/exemptions will be granted for protocol inclusion/exclusion criteria.

Subjects are included in the study if they meet all of the following criteria:

- Written informed consent provided by the patient
- Age ≥ 18 years
- Chronic Atopic Dermatitis present for at least 3 years
- Disease is not responsive to topical medications, or for whom topical treatments are not indicated or desired
- Willing and able to comply with all clinic visits and study-related procedure
- EASI score ≥ 16 at screening and baseline visits
- IGA score \geq 3 at screening and baseline visits
- $\geq 10\%$ body surface area (BSA) of AD involvement at screening and baseline visits
- Documented recent history (within 6 months before the screening visit) of inadequate response to treatment with topical medications or for whom topical treatments are otherwise medically inadvisable or undesired

4.2 EXCLUSION CRITERIA

Subjects will be excluded from the study if they meet any of the following criteria:

- Treatment with an investigational drug within 8 weeks of baseline visit
- Having received the following treatments within 4 weeks before the baseline visit, or any condition that, in the opinion of the investigator, is likely to require such treatment(s) during the first 4 weeks of study treatment:
 - a. Immunosuppressive/immunomodulating drugs (eg, systemic corticosteroids, cyclosporine, mycophenolate-mofetil, IFN-γ, Janus kinase inhibitors, azathioprine, methotrexate, etc.)
 - b. Phototherapy for AD
- Treatment with topical corticosteroids (TCS) or topical calcineurin inhibitors (TCI) within 1 week before the baseline visit
- Initiation of treatment during the screening period with prescription moisturizers or moisturizers containing additives such as ceramide, hyaluronic acid, urea, or filaggrin degradation products during the screening period (patients may continue using stable doses of such moisturizers if initiated before the screening visit)
- Regular use (more than 2 visits per week) of a tanning booth/parlor within 4 weeks of the screening visit
- History of severe allergic or anaphylactic reactions to monoclonal antibodies
- Administration of any live (attenuated) vaccine within 4 weeks prior to the baseline
- Any history of dysplasia or history of malignancy (including lymphoma and leukemia) other than a successfully treated non-metastatic cutaneous squamous cell carcinoma, basal cell carcinoma or localized carcinoma in situ of the cervix
- Active chronic or acute infection requiring treatment with systemic antibiotics, antivirals, antiparasitics, antiprotozoals, or antifungals within 2 weeks before the baseline visit, or superficial skin infections within 1 week before the baseline visit. NOTE: patients may be rescreened after infection resolves
- Known or suspected history of immunosuppression, including history of invasive opportunistic infections (eg, tuberculosis [TB], histoplasmosis, listeriosis, coccidioidomycosis, pneumocystosis, aspergillosis) despite infection resolution: or unusually frequent, recurrent, or prolonged infections, per investigator judgment
- History of human immunodeficiency virus (HIV) infection or positive HIV serology at screening
- Positive with hepatitis B surface antigen (HBsAg) or hepatitis C antibody at the screening visit
- Presence of skin comorbidities that may interfere with study assessments

- Severe concomitant illness(es) that, in the investigator's judgment, would adversely affect the patient's participation in the study. Examples include, but are not limited to, patients with short life expectancy, patients with uncontrolled diabetes (HbA1c ≥ 9%), patients with cardiovascular conditions (eg, stage III or IV cardiac failure according to the New York Heart Association classification), severe renal conditions (eg, patients on dialysis), hepato-biliary conditions (eg, Child-Pugh class B or C), neurological conditions (eg, demyelinating diseases), active major autoimmune diseases (eg, lupus, inflammatory bowel disease, rheumatoid arthritis, etc.), other severe endocrinological, gastrointestinal, metabolic, pulmonary or lymphatic diseases. The specific justification for patients excluded under this criterion will be noted in study documents (chart notes, case report forms [CRFs], etc.)
- Pregnant or breastfeeding women, or women planning to become pregnant or breastfeed during the study
- Where relevant, women unwilling to use adequate birth control

5. TREATMENT PLAN

5.1 STUDY PROCEDURES

Screening

The screening period begins once the informed consent is signed (Max 14 days).

- Informed Consent
- Demographics
- Medical History
- Concomitant Medications/Treatments
- Physical Examination
- Vital Signs (blood pressure, pulse, oxygen saturation, respiratory rate and body temperature)
- Height
- Weight
- Body Mass Index (BMI) [BMI= weight (kg)/height (m²)]
- EASI
- IGA
- SCORAD
- Blood Draw, 21mL:
 - Chemistry panel: Albumin, Alkaline Phosphatase, ALT, AST, GGT, Bicarbonate (CO2) Calcium, Chloride, Creatinine, Glucose, Potassium, Sodium, Total Bilirubin, Total Protein, Urea Nitrogen, 8.5 mL blood
 - Hematology Panel: Complete Blood Count (CBC) with differential and platelets, 4.0 mL blood
 - Infectious disease screening: HIV antibody, Hepatitis C antibody, Hepatitis B panel (HBsAg, anti-HBc, anti-HBs), and interferon gamma release assay (IGRA), 8.5 mL blood
 - Serum pregnancy test for WOCBP, 8.5 mL blood
- Pruritus/Pain NRS: the baseline level of itching and pain will be recorded. Patients will be given a study diary that has the NRS (0-10 scale) for days 0 to 35. The patient will be instructed to complete the scale daily (three questions, each on a 0-10 scale). The patient should bring this diary to all subsequent visits for review by the site staff.

Visit 1 (Day 0)

> At least 45 minutes before injection: When using pre-filled syringes, remove syringe from

refrigeration and lay flat; allow to warm to room temperature. Do not heat

Pre-injection

- o Concomitant medications/treatments
- o Urinalysis
- Electrocardiogram (ECG) (patient should be supine for at least 5 minutes prior to performating ECG)
- o DLQI
- Urine pregnancy
- o EASI
- o IGA

- HADS
- Pruritus/Pain NRS: data from patient diary to be recorded at this time if available
- o SCORAD
- POEM
- o GISS
- Blood draw:
 - PK and Biomarker Analysis, 6mL
- Visit 1 Questionnaire, Part 1: Pruritus, Pain and Erythema
- Vital signs (blood pressure, pulse, oxygen saturation, respiratory rate and body temperature)

Bermekimab subcutaneous injection in accordance with injection site determined by BMI at Screening

Post bermekimab subcutaneous injection

- ➤ 1 hour monitoring post-injection
 - Injection reaction
 - Vital signs (blood pressure, pulse, oxygen saturation, respiratory rate and body temperature) one hour post injection (70 +/- 10 minutes)
 - Visit 1 Questionnaire, Part 2: Pruritus, Pain and Erythema—data from this form must be recorded one hour post-injection (70 +/- 10 minutes)
- Adverse event monitoring

Visit 2 (Day 7 +/-2)

> At least 45 minutes before injection: When using pre-filled syringes, remove syringe from

refrigeration and lay flat; allow to warm to room temperature. Do not heat

Pre-injection

- o Concomitant medications/treatments
- o DLQI
- Urine pregnancy
- o EASI
- o IGA
- o HADS
- Pruritus/Pain NRS: data from patient diary to be recorded at this time if available
- o SCORAD
- o POEM
- o GISS
- Vital signs (blood pressure, pulse, oxygen saturation, respiratory rate and body temperature)

Bermekimab subcutaneous injection in accordance with injection site determined by BMI at Screening

Post bermekimab subcutaneous injection

- ➤ 1 hour monitoring post-injection
 - Injection reaction
 - Vital signs (blood pressure, pulse, oxygen saturation, respiratory rate and body temperature) one hour post injection (70 +/- 10 minutes)
- Adverse event monitoring

Visit 3 (Day 14 +/-2)

> At least 45 minutes before injection: When using pre-filled syringes, remove syringe from

refrigeration and lay flat; allow to warm to room temperature. Do not heat

Pre-injection

- Concomitant medications/treatments
- o DLQI
- Urine pregnancy
- o EASI
- o IGA
- o HADS
- Pruritus/Pain NRS: data from patient diary to be recorded at this time if available
- o SCORAD
- o POEM
- o GISS
- Blood draw:
 - chemistry and hematology, 12.5mL
 - PK and Biomarker Analysis, 6mL
- Vital signs (blood pressure, pulse, oxygen saturation, respiratory rate and body temperature)

Bermekimab subcutaneous injection in accordance with injection site determined by BMI at Screening

Post bermekimab subcutaneous injection

- ➤ 1 hour monitoring post-injection
 - Vital signs (blood pressure, pulse, oxygen saturation, respiratory rate and body temperature) one hour post injection (70 +/- 10 minutes)
- Adverse event monitoring

Visit 4 (Day 21 +/-2)

> At least 45 minutes before injection: When using pre-filled syringes, remove syringe from

refrigeration and lay flat; allow to warm to room temperature. Do not heat

Pre-injection

- Concomitant medications/treatments
- o Urinalysis
- o DLQI
- Urine pregnancy
- o EASI
- o IGA
- HADS
- Pruritus/Pain NRS: data from patient diary to be recorded at this time if available
- o SCORAD
- o POEM
- o GISS
- Vital signs (blood pressure, pulse, oxygen saturation, respiratory rate and body temperature)

Bermekimab subcutaneous injection in accordance with injection site determined by BMI at Screening

Post bermekimab subcutaneous injection

- 1 hour monitoring post-injection
 - Injection reaction
 - Vital signs (blood pressure, pulse, oxygen saturation, respiratory rate and body temperature) one hour post injection (70 +/- 10 minutes)
- Adverse event monitoring

Visit 5 (day 28 +/-2)

> At least 45 minutes before injection: When using pre-filled syringes, remove syringe from

refrigeration and lay flat; allow to warm to room temperature. Do not heat

Pre-injection

- Concomitant medications/treatments
- Physical Examination
- o DLQI
- Urine pregnancy
- o EASI
- o IGA
- HADS
- Pruritus/Pain NRS: data from patient diary to be recorded at this time if available
- o SCORAD
- o POEM
- o GISS
- Blood draw:
 - chemistry and hematology, 12.5mL
 - PK and Biomarker Analysis, 6mL
- Vital signs (blood pressure, pulse, oxygen saturation, respiratory rate and body temperature)

Bermekimab subcutaneous injection in accordance with injection site determined by BMI at Screening

Post bermekimab subcutaneous injection

- ➤ 1 hour monitoring post-injection
 - Injection reaction
 - Vital signs (blood pressure, pulse, oxygen saturation, respiratory rate and body temperature) one hour post injection (70 +/- 10 minutes)
- Adverse event monitoring

Visit 6 (day 35 +/-2)

> At least 45 minutes before injection: When using pre-filled syringes, remove syringe from

refrigeration and lay flat; allow to warm to room temperature. Do not heat

Pre-injection

• Concomitant medications/treatments

- o DLQI
- Urine pregnancy
- EASI
- o IGA
- HADS
- Pruritus/Pain NRS: data from patient diary to be recorded at this time if available
- o SCORAD
- POEM
- o GISS
- Vital signs (blood pressure, pulse, oxygen saturation, respiratory rate and body temperature)

Bermekimab subcutaneous injection in accordance with injection site determined by BMI at Screening

Post bermekimab subcutaneous injection

- ➤ 1 hour monitoring post-injection
 - Injection reaction
 - Vital signs (blood pressure, pulse, oxygen saturation, respiratory rate and body temperature) one hour post injection (70 +/- 10 minutes)
- Adverse event monitoring

Visit 7 (day 42 +/-2)

> At least 45 minutes before injection: When using pre-filled syringes, remove syringe from

refrigeration and lay flat; allow to warm to room temperature. Do not heat

Pre-injection

- Concomitant medications/treatments
- o DLQI
- Urine pregnancy
- o EASI
- o IGA
- HADS
- Pruritus/Pain NRS: data from patient diary to be recorded at this time if available
- o SCORAD
- o POEM
- o GISS
- Vital signs (blood pressure, pulse, oxygen saturation, respiratory rate and body temperature)

Bermekimab subcutaneous injection in accordance with injection site determined by BMI at Screening

Post bermekimab subcutaneous injection

- 1 hour monitoring post-injection
 - Injection reaction
 - Vital signs (blood pressure, pulse, oxygen saturation, respiratory rate and body temperature) one hour post injection (70 +/- 10 minutes)
- Adverse event monitoring

Visit 8 (day 49 +/- 2)

> *At least 45 minutes before injection*: When using pre-filled syringes, remove syringe from

refrigeration and lay flat; allow to warm to room temperature. Do not heat

Pre-injection

- Concomitant medications/treatments
- Urinalysis
- Electrocardiogram (ECG) (patient should be supine for at least 5 minutes prior to performating ECG)
- Physical Examination
- o DLQI
- Urine pregnancy
- o EASI
- o IGA
- o HADS
- Pruritus/Pain NRS: data from patient diary to be recorded at this time if available
- o SCORAD
- o POEM
- o GISS
- Blood draw:
 - chemistry and hematology, 12.5mL
 - PK and Biomarker Analysis, 6mL
- Vital signs (blood pressure, pulse, oxygen saturation, respiratory rate and body temperature)

Bermekimab subcutaneous injection in accordance with injection site determined by BMI at Screening

Post bermekimab subcutaneous injection

- ➤ 1 hour monitoring post-injection
 - Injection reaction
 - Vital signs (blood pressure, pulse, oxygen saturation, respiratory rate and body temperature) one hour post injection (70 +/- 10 minutes)
- Adverse event monitoring

Visit 9 (56 +/- 2)

- Concomitant medications/treatments
- > DLQI
- Physical Examination
- ► EASI
- ► IGA
- > HADS
- > Pruritus/Pain NRS: patient diary to be retained and data to be recorded
- > SCORAD
- > POEM
- ➢ GISS
- Vital signs (blood pressure, pulse, oxygen saturation, respiratory rate and body temperature)
- Adverse Event Monitoring

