3.1 STUDY ENDPOINTS

Primary Endpoint:

• Safety and Tolerability

Secondary Endpoints:

- Change in Eczema Area and Severity Index Score (EASI) from baseline to visit 8 EASI score will assess severity and extent of AD with respect to erythema, excoriation, infiltration and lichenification at 4 anatomic sites of the body: lower and upper extremities, trunk and head. The total EASI score shall be in a range (from 0 to 72 points (from no disease to maximum disease severity, respectively).
- Patients (%) achieving Investigator's Global Assessment (IGA) Response (0 or 1) at Visit
 - 8

IGA assesses disease severity and clinical response using a 5-point scale: 0 = clear; 1 = almost clear; 2 = mild; 3 = moderate; 4 = severe. The score is determined by ranking the extent of erythema and papulation/infiltration. A clinical response to therapy will be an IGA score of 0 (clear) or 1 (almost clear). Patients receiving more than one treatment with additional medication to treat AD exacerbation during the study or missing IGA scores at Visit 8 will be treated as non-responders.

- Patients (%) achieving ≥2 IGA Score Reduction at Visit 8
- Pharmacokinetics (PK) Assessment

An enzyme-linked immunosorbent assay (ELISA) has been developed to specifically measure bermekimab levels in human plasma. Blood will be drawn into a single 6 ml Na-Heparin collection tube at each PK collection time point (sample collection is pre-dose at visit 1, visit 3, visit 5, and visit 8). These samples will be collected per the study lab manual and immediately shipped to the Sponsor for PK analysis. The PK samples will also be used to test for the presence of antibodies against bermekimab.

- Change (%) for peak weekly averaged pruritus numerical rating scores (NRS) from baseline to visit 8
- The NRS rating system captures the intensity of patient's itch and pain over a 24-hour period. The following question will be presented to patients: "how would a participant rate his or her itch at the worst moment and on average during the previous 24 hours (scale 0 10 [0 = no itch; 10 = worst possible itch])?" and "how would you rate your pain on average during the previous 24 hours [0 = no pain; 10 = severe pain])?

```
CONFIDENTIAL
```

- Change in weekly averaged peak NRS from baseline to visit 8
- Change in SCORing Atopic Dermatitis (SCORAD) score from baseline to visit 8
 SCORAD was developed by the European Task Force on Atopic Dermatitis

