5.2 STUDY CALENDAR

Visit	Screen	1	2	3	4	5	6	7	8	9
Study Day		0	7 ±2	14 ± 2	21 ±2	28 ± 2	35 ± 2	42 ± 2	49 ± 2	56 ± 2
Informed Consent	Х									
Demography, Height, Weight ^f	х									
Medical History	х									
Infectious Disease Panel +	Х									
IGRA ^e	х									
Serum Pregnancy	Х									
Physical Examination	Х					Х			Х	Х
Urinalysis ▲		Х			Х				х	
Electrocardiogram (ECG)£		Х							Х	
Visit 1 Questionnaire ◆		Х								
Vital Signs ⁺	Х	Х	Х	Х	Х	Х	Х	Х	Х	Х
Urine Pregnancy		Х	х	Х	Х	х	Х	Х	х	
Blood Draw	x ^{ab}	x ^c		xabc		xabc			xabc	
Bermekimab Injection �		Х	Х	Х	Х	Х	Х	Х	Х	
EASI	Х	Х	х	х	Х	х	х	х	х	х
IGA	Х	Х	Х	Х	Х	Х	Х	Х	Х	Х
SCORAD	Х	Х	х	Х	Х	х	Х	Х	Х	Х
DLQI		Х	х	х	Х	х	х	х	х	х
Pruritus/pain NRS ^d		Х	Х	Х	Х	Х	Х	Х	Х	Х
POEM		Х	х	Х	Х	х	Х	Х	х	х
GISS		Х	Х	Х	Х	Х	Х	Х	Х	Х
HADS		X	х	X	Х	X	X	X	X	X
Adverse Events		Х	х	Х	Х	X	Х	Х	Х	х
Concomitant	X	X	х	х	X	х	X	X	Х	х
Meds/Treatments*										

^a Chemistry Panel including: Albumin, Alkaline Phosphatase, ALT, AST, GGT, Bicarbonate (CO2) Calcium,

Chloride, Creatinine, Glucose, Potassium, Sodium, Total Bilirubin, Total Protein, Urea Nitrogen

^b Hematology Panel including: Complete whole blood (WBC, HgB, Platelet, differential)

^cBlood draw for PK and Biomarker analysis

^d Data from patient diary for the previous 7 days to be recorded at this time.

^e Interferon gamma release assay

^fBMI will be calculated at this visit using height and weight

+HIV antibody, Hepatitis C antibody, Hepatitis B panel (HBsAg, anti-HBc, anti-HBs), and interferon gamma release assay (IGRA)

▲ Urinalysis will assess pH, protein, glucose, and blood cells

 \pounds A standard 12-lead ECG will be performed. The ECG strips and/ or reports will be retained with the source documentation.

✤ Each bermekimab injection will be followed by 1 hour monitoring for injection site reaction and vital signs 1 hour post injection (70+/- 10 minutes)

⁺ Vital signs include blood pressure, pulse, oxygen saturation, respiratory rate and body temperature

✦ Assessment of patients Pruritus, Pain and Erythema will be recorded twice [once pre-injection, once post-injection of bermekimab] during visit 1.

* Concomitant medications within 30 days before screening until 7 days after the last administration of the study drug must be recorded for the purpose of drug-drug and drug-disease interaction evaluation and signal detection.

BMI: Body Mass Index [BMI= weight (kg)/height (m²)]
IGRA: Interferon Gamma Release Assay
DLQI: Dermatology Life Quality Index

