8. STUDY VARIABLES

8.1 DEMOGRAPHIC AND DISEASE CHARACTERISTICS

Demographic characteristics will include standard demography (age, sex, race, weight, and BMI), medical history, medication history, and prior biologic use for each patient. Characteristics of the patient's atopic dermatitis, including duration of disease, baseline EASI score (including individual signs score), baseline Investigator's Global Assessment, baseline body surface area involvement, baseline pruritus numerical rating score, baseline SCORAD score, baseline patient oriented eczema measure, baseline DLQI, and baseline HADS score, will be collected. *Baseline is defined as the visit 1 pre-injection assessment*.

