The SCORAD is a validated tool used in clinical research and clinical practice that was developed to standardize the evaluation of the extent and severity of AD. There are 3 components to the assessment: A = extent or affected body surface area, B = intensity, and C = subjective symptoms. The extent of AD is assessed as a percentage of each defined body area and reported as the sum of all areas, with a maximum score of 100% (assigned as "A" in the overall SCORAD calculation). The intensity of 6 specific symptoms of AD (redness, swelling, oozing/crusting, excoriation, skin thickening/ lichenification, dryness) is assessed using the following scale: none (0), mild (1), moderate (2), or severe (3) (for a maximum of 18 total points, assigned as "B" in the overall SCORAD calculation). Subjective assessment of itch and sleeplessness is recorded for each symptom by the patient or relative on a VAS, where 0 is no itch (or sleeplessness) and 10 is the worst imaginable itch (or sleeplessness), with a maximum possible score of 20. This parameter is assigned as "C" in the overall SCORAD calculation. The SCORAD is calculated as: A/5 + 7B/2 + C where the maximum is 103.

Patient Assessment of Pruritus and Pain

The NRS is a simple assessment tool that patients will use to report the intensity of their pruritus (itch) and pain during a daily recall period using a study diary. Patients will be asked to complete the following questions:

- For average itch intensity: "On a scale of 0 to 10, with 0 being 'no itch' and 10 being the 'worst itch imaginable', how would you rate your itch **on average** during the previous 24 hours?"
- For maximum itch intensity: "On a scale of 0 to 10, with 0 being 'no itch' and 10 being the 'worst itch imaginable', how would you rate your itch at the **worst moment** during the previous 24 hours?"
- For pain intensity: "On a scale of 0 to 10, with 0 being 'no pain' and 10 being the 'most severe pain', how would you rate your pain **on average** during the previous 24 hours?"

Patients will be instructed to record their NRS score daily from day 0 to day 56 (+/-2). Sites will be expected to review the diary at each visit and enter the data from the previous 7 days.

Visit 1 Questionnaire for Pruritus, Pain and Erythema

The following questions assess the intensity of pruritus (itch) and pain experienced by the patient before and after the injection of bermekimab during visit 1. The patient will answer the following questions:

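### The NRS diary starts on the day of the first injection, so it cannot supply the pre-dose weekly average that the itch endpoints need, and its end day differs between sections with no group named

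*Combined protocol and SAP*

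**What the plan says.** Two sections describe the diary. Section 5.1 (Screening) says "Patients will be given a study diary that has the NRS (0-10 scale) for days 0 to 35". Section 8.2 says "Patients will be instructed to record their NRS score daily from day 0 to day 56", with a two-day tolerance. Both start on day 0, which section 5.1 identifies as visit 1, the first injection. Neither names a dose group.

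The calendar in section 5.2 marks pruritus/pain NRS at visits 1 to 9 but not at screening. Its footnote d reads "Data from patient diary for the previous 7 days to be recorded at this time". Section 8.2 gives sites the same task: "Sites will be expected to review the diary at each visit and enter the data from the previous 7 days".

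Section 3.1 lists "Change in weekly averaged peak NRS from baseline to visit 8" and a percent-change version as secondary endpoints. Section 8.1 states that "Baseline is defined as the visit 1 pre-injection assessment".

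Two further statements bear on the point. Section 5.1 has a baseline level of itch and pain recorded at screening, without saying which question or period it covers. At visits 1 to 8 it has diary data recorded only where they exist.

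On follow-up, section 3 takes the 200 mg group (Group A) to day 35 over 6 visits and the 400 mg group (Group B) to day 56 over 9 visits. Visit 9 in section 5.1 still expects the diary: "Pruritus/Pain NRS: patient diary to be retained and data to be recorded".

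**The concern.** The endpoint wording, footnote d and the site entry rule together imply a pre-dose week of daily scores. The diary that patients are told to fill in does not cover that week. If sites follow the stated range, there is no weekly-average baseline and no rule for what replaces it. The natural substitute, the day 0 rating, would be subtracted from a 7-day mean at visit 8. That is not the quantity the endpoint names, and it is noisier. The day 0 entry might also be made after the injection, and it falls within the 7 days before visit 2 (days 0 to 6). Pre-dose days that were never recorded cannot be recovered at analysis.

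The end day raises a second, separate question. Sections 5.1 and 8.2 give different end days as if for everyone. A Group B patient handed the shorter diary would have no visit 8 weekly score, which is the other half of the same change.

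**Working it through.** **Diary days available.** The plan states no figure on this point, so I counted days. The 7 days before a visit on day D are D-7 to D-1. Visit windows are ±2 days after visit 1.

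| Visit (day range) | Diary days 0–35 | Diary days 0–56 |
|---|---|---|
| 1 (0) | 0 of 7 | 0 of 7 |
| 6 (33–37), last for Group A | 6–7 of 7 | 7 of 7 |
| 7 (40–44) | 0–3 of 7 | 7 of 7 |
| 8 (47–51) | 0 of 7 | 7 of 7 |

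Visit 1 needs days -7 to -1, and none lies in either range. If the week is counted as ending on the visit day, visit 1 has 1 of 7, provided the entry precedes the injection. For visit 8, the earliest needed day is 47 - 7 = 40, already past day 35. In the other direction, a day 56 end for everyone would ask Group A for 56 - 35 = 21 entries after its last visit.

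**Effect on precision.** The documents give no SDs or correlations, so these are assumptions: day-to-day SD sw = 1.5, SD of true change sc = 2.0, and correlation between days k apart of rho^k, with rho 0.5 to 0.7. Noise at baseline and at visit 8 is taken as independent.

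- Variance of an n-day mean = sw² × v_n, where v_n = (1/n)[1 + 2 Σ(1 - k/n) rho^k], k = 1 to n-1. This gives v_7 = 0.348 at rho 0.5 and 0.518 at rho 0.7.
- Single-day baseline: Var(change) = sc² + sw²(1 + v_7).
- Weekly baseline: Var(change) = sc² + 2 sw² v_7.

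At rho 0.5: √(4 + 2.25 × 1.348) = 2.65 against √(4 + 4.5 × 0.348) = 2.36, ratio 1.12.

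At rho 0.7: √(4 + 2.25 × 1.518) = 2.72 against √(4 + 4.5 × 0.518) = 2.52, ratio 1.08.

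For Group B (n = 20), the 95% half-width is 2.093 × SD/√20: 1.24 against 1.10 points at rho 0.5, and 1.27 against 1.18 at rho 0.7.

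With sw from 1 to 2 and sc from 1.5 to 2.5, the interval is 5 to 23% wider at rho 0.5 and 3 to 14% wider at rho 0.7, so 3 to 23% overall.

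Percent change was simulated at the same two correlations with sw = 1.5 and sc = 2.0. Scores were limited to 0–10, baseline SD was 1.5, baseline mean 6 to 8 and mean change -1.5 to -3.5; patients with either baseline below 2 were excluded. The interval is about 7 to 17% wider.

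The model treats itch as stable in the week before dosing. Section 4.2 excludes topical corticosteroids and calcineurin inhibitors in that week, so drift is possible. A linear drift of 0.5 to 1.0 points over the week (assumed) would move a day 0 rating 4/7 of that, or 0.29 to 0.57 points, away from the 7-day mean.

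**The case against.** The strongest reply is that the plan's intent is clear and practice may follow it. Patients receive the diary at screening, are told to complete it daily and bring it to every later visit, and footnote d asks for the prior week at visit 1. A careful site could therefore collect the pre-dose week. That stands as a reason to treat the loss as conditional. It does not remove the conflict, because the diary described in section 5.1 has scales only from day 0, and sites may differ on when entries begin.

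The plan also has other pre-dose itch ratings. The screening level is one, but it is not described as a weekly mean, the calendar does not mark it, and section 8.1 places baseline at visit 1. The Visit 1 Questionnaire asks about current intensity, not the worst moment in 24 hours, so it cannot stand in for a peak score. The allowance for absent diary data applies at visits 1 to 8 alike. It tolerates gaps and does not ask for pre-dose entries.

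Because each question looks back 24 hours, a day 0 entry made before injection does describe the last pre-dose day. That is still one day, not seven.

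On the end day, 35 and 56 match the two groups' follow-up, so the intended assignment is easy to guess. No text makes it.

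Finally, the precision loss is small in the base case, 0.09 to 0.14 NRS points of half-width at n = 20. It would be smaller still if days were more strongly correlated (1 to 5% at rho 0.9 over the same SDs). I accept this: the case rests on the contradiction and the undefined baseline, not on the width of an interval.

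**Conclusion.** The conflict holds on the text. Followed as written, the diary yields 0 of the 7 days before visit 1, so the weekly-average baseline does not exist and the change compares a single rating with a 7-day mean. A Group B patient given the day 0 to 35 diary would also have no visit 8 weekly score. Under the assumed SDs, the interval for mean change is about 8 to 12% wider, with a range of 3 to 23%.

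A reader might infer more: that the trial will have no pre-dose itch data, that Group B will certainly lose its visit 8 scores, or that the NRS results will be seriously imprecise. The documents do not support these readings. A day 0 rating and a screening level are both available, section 8.2 and the calendar run to day 56, and the precision loss is modest on any plausible correlation.

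Safety is the primary endpoint. The NRS endpoints are secondary and descriptive, the sample is one of convenience, and no decision rule depends on them. This should be fixed, at low priority. That Group A has no visit 8 at all is a separate issue.

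**What to change.** In sections 5.1, 5.2 and 8.2:

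- Start daily NRS entries at least 7 days before visit 1. The diary is already handed out at screening.
- Define the NRS baseline as the mean of the available daily scores in the 7 days before the first injection, and the visit 8 value as the mean of the 7 days before visit 8. State the same minimum number of days for both. Section 5.1 sets only a maximum of 14 days for screening, so the minimum also settles what happens when screening is short.
- Say that the screening rating is not the endpoint baseline.
- State the diary end day by group, matching each group's last visit in section 3: day 35 for Group A and day 56 for Group B.

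The cost is a reprinted diary, wording in three sections, and about 7 (at most 14) extra diary days per patient. No visits are added, and no entries are asked for after either group's last scheduled visit.
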